Appendix C (The IRB-approved Protocol)

Additional questions are designed to address several aspects of the children's dietary habits related to chemical exposures, including information about the number of meals prepared in the home versus elsewhere, exposure-relevant food types (commodities/groups, e.g., dairy, green vegetables, meat), food forms (fresh versus processed), and sources of purchased groceries (e.g., supermarket versus farmer's market).

Finally, the questionnaire includes a number of questions designed to be used in conjunction with the data collected from the housing and community information questions. These include queries about the distance of all locations visited (e.g., parks) from the home, use of outdoor locations at home, the caregiver's perception of the general safety of their children in the locations visited, sleep quality of the child, and the use of public transportation.

The Green Housing Study questionnaires collect considerable information on housing factors. In order to better understand children's exposure factors, additional information will be collected, including technician observations of flooring and furnishings in each room, technician ratings of clutter and cleanliness, and information on the exterior area of the residential complex. The interior metrics will be used to assess the predictability of chemicals in house dust and as additional information for activity-exposure modeling. The exterior metrics (activity areas and surface types) will be used in assessments of child contact with soil, activity-exposure modeling, and the potential for residential track-in of measured chemicals.

Residential location information and selected activity information about the child's interaction with the larger community will be collected. Geospatial location of the residence will be used in the assessment of community attributes for domains that may be important for children's exposure to chemicals and for metrics of potentially important co-exposures and stressors; community-level domains may include pollutant sources such as roads and point sources, walkability, crime/violence, access to parks and food, neighborhood socioeconomic status, and other extant metrics depending on the study location. This information will not be collected through interaction with study participants – it will be obtained from extant data and geodata sources.

Information on usage frequency of household cleaning products and personal care products will be collected as part of the questionnaire. These questions are based on participant recall and cover typical cleaning and personal care activities carried out by any of the household residents. This section consists of three parts: (1) questions on the use of products in nine consumer product categories; (2) questions on specific types of household cleaning products; and (3) questions on specific types of personal care products.

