Appendix C (The IRB-approved Protocol)

Primary objectives:

- 1) Identify and characterize factors affecting children's exposures to chemical ingredients from consumer products found in their everyday environment in order to support the data and modeling needs of the exposure components of EPA's national research programs;
- 2) Evaluate the pilot study data metrics for incorporation in and enhancement of CDC's ability to understand the relationship between environmental exposures and asthma in green versus traditional low-income housing;
- 3) Compare multimedia measurements and survey data between pre- and post-renovation time points in green and traditional low-income housing to assess exposure related changes in the residence and participants due to renovation activities.

Objective 1 will examine how influential personal, housing, and community factors are in determining children's exposures. Results will be used to directly compare siblings and determine how personal and housing factors vary. For siblings living in the same household, we hypothesize that shared exposures to housing and community factors both before and after building renovation will be similar. Thus, we hypothesize that personal exposure factors, including activities and behaviors, will most influence exposure to chemical and biological agents found in their indoor environment. Furthermore, the variability in personal exposure factors will be a function of age, lifestage, and health status (asthma versus no asthma). We can use this information to parameterize, refine, and evaluate exposure and dose models for consumer product active ingredients. Because of the lack of data on personal, housing, and community factors from the same cohort, it is necessary to collect these data to evaluate this objective.

Objective 2 will evaluate the pilot study methods and approaches for measuring exposures to consumer product chemicals and identifying exposure factors. It will also establish suitability for incorporation in future Green Housing Study sites and for future research directions. Our data collection effort is intended to complement the multimedia measurements and information being collected by CDC in the Green Housing Study. Methods found to be suitable in the pilot study will allow EPA and CDC to improve the evaluation of relationships between environmental exposures and asthma in the renovated and non-renovated homes.

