Appendix C (The IRB-approved Protocol)

4.5 Questionnaire

One questionnaire will query participants on location, transportation, activity, diet, and consumer products use and will be used by the field staff to record home observations (Appendix C). It will complement the questionnaires currently being used in the Green Housing Study and will be administered using a conventional pen and paper approach to the mother/caregiver for the index child and participating sibling(s). The questionnaire is primarily a recall questionnaire covering the activities of the index child and sibling(s) on the day prior to each field visit. Figure 2 shows the data flow for the questionnaire.

Figure 2.

Questions will gather information on the types of locations the children visited throughout the day, including residences, non-residential indoor environments (e.g., schools and stores), and outdoor environments. In order to reduce burden, questions will be asked about the 5 locations where each child spent the most total time. A series of transportation questions will also be asked related to how the children moved from one location to another to characterize time spent in vehicles or other near-road locations (e.g., street or bus stop). Questions will also ask about the types of activities performed in each location, with a primary focus on activities relevant to exposure to consumer products (e.g., bathing or grooming activities, chores, and contact with pets); however, other general categories of activities are included for estimating an overall level of energy expenditure for each child relevant to intake dose rates of indoor chemicals.

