Appendix C (The IRB-approved Protocol)

house dust loading measurements or personal samples in order to model children's soil and dust ingestion rates (objective 10). Finally, the interaction of time spent in different locations with housing and community factors such as crime rate, transportation options, and perception of children's safety will be quantified.

From the activity survey results, descriptive statistics of reported time spent in microenvironments and activities will be calculated. In addition, GPS-based time spent in microenvironments will be calculated using EPA's MicroTrac model (Breen et al., 2014). This model takes as input a GPS time-series and a general location of the participant's home and using a computational algorithm calculates time spent at home and in travel (in vehicles). The MicroTrac results will be compared with the survey results as in Breen et al. (2014). Differences among age groups, genders, and asthmatic/non-asthmatic children for both survey and GPS results will be quantified and tested using appropriate parametric or non-parametric techniques.

Children's activities are an important determinant of the types and amounts of chemicals encountered (McCurdy, 2000). Therefore, time spent in exposure-relevant activities (e.g., time spent with pet or exercising) will be characterized via standard methods (Xue et al., 2004). A primary analysis will evaluate age- and asthma-dependent differences in activity level in children living in the same household. The results from this analysis will aid in characterizing/elucidating the contributions of age, health, socioeconomic status, and other factors to describe the variability in activity levels. Similar to location, the interaction between housing and community factors (e.g., crime or noise pollution) and exposure relevant activities will be addressed. In addition, the location of high-dose rate activities (e.g., exercise) for these children will be compared to other, previously studied child cohorts to assess the influence of community or socioeconomic status-driven factors (such as distance from pollutant sources, or indoor versus outdoor exercise locations).

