Appendix C (The IRB-approved Protocol)

B. Location Questions (To be completed by field technician and participant)

3. For each approximate time period given below, indicate where your child was located. Select any locations that apply to the time period.

	Home	Outdoor area at home	Other residence (ex. babysitter's house)	Store	Restaurant	Church	Other indoor location	Park	Bus/train stop	On or near street	Parking garage	Other outdoor location	In vehicle	Don't know/Refused to answer
5:00 am - 5:29 am														
5:30 am - 5:59 am														
6:00 am - 6:29 am														
6:30 am - 6:59 am														
7:00 am - 7:29 am														

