Appendix C (The IRB-approved Protocol)

E. Household Cleaning Products (To be completed by field technician and participant)

21. Please select use frequency for each product type inside your home

	Daily	Weekly	Monthly	Yearly/ Never
All-purpose cleaner				
Glass cleaner				
Floor cleaner				
Toilet bowl cleaner				
Carpet cleaner				
Polish or wax				
Air freshener				
Disinfectant Spray				
Laundry detergent				
Dryer sheets				
Stain/spot remover				

F. Personal Care Products (To be completed by field technician and participant)

22. Please select use frequency for each product type inside your home

	Daily	Weekly	Monthly	Yearly/ Never
Shampoo				
Liquid hand soap				
Hand sanitizer				
Hand/body lotion				
Facial moisturizer				
Fragrance/perfume				
Hair styling products				
Sunscreen				

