Appendix C (The IRB-approved Protocol)

G. Consumer Product Classes (To be completed by field technician and participant)

23. Please select use frequency for each product type inside/near your home

	Daily	Weekly	Monthly	Yearly/ Never
Arts and Crafts Products				
Automotive Products				
Home Maintenance				
Cleaning Products				
Personal Care Products				
Pesticides				
Pet Care Products				
Home Office				
Landscape and Yard				

H. Home Observations (To be completed by field technician with input from participant as needed)

24a. Select the answer(s) that best describe the percentage of total floor area in the home.

	0	1-20	21-40	41-60	61-80	81-100
% Covered by carpet or rug						
% Exposed linoleum or linoleum tile						
% Exposed wood or wood laminate						
% Exposed ceramic or stone tile						
% Exposed other						

24b. If a percentage of the floor was "Other," what was the material?

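### The approved questionnaire lacks several items that section 4.5 says it contains, asks about product use only for the home, and merges yearly users with never-users

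*Protocol*

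**What the plan says.** **Section 4.5** describes one questionnaire, answered by the mother or caregiver for the index child and for the sibling. Among location types it lists "non-residential indoor environments (e.g., schools and stores". It also announces questions on how the children got from place to place, how far visited places are from home, how safe the caregiver judges those places to be, and public-transport use. The product-use questions, it says, "cover typical cleaning and personal care activities carried out by any of the household residents".

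**Appendix C (the approved questionnaire)** is headed with one child's age and gender.

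- Item 3 begins "For each approximate time period given below, indicate where your child was located" and gives a half-hourly grid of places.
- Items 21 (cleaning products) and 22 (personal care products) both read "Please select use frequency for each product type inside your home".
- Item 23 (nine product classes) reads "Please select use frequency for each product type inside/near your home".
- Items 21 to 23 offer four answers: daily, weekly, monthly, or a single category for yearly and never together.

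**The objectives** rely on this instrument.

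- Section 2.2, Objective 1, hypothesises for siblings sharing a home that "personal exposure factors, including activities and behaviors, will most influence exposure to chemical and biological agents" found indoors.
- Section 5.0, Objectives 4 and 5, uses reported frequency of product use to predict or compare concentrations.
- Section 5.0, Objective 8, plans to quantify how time in different locations interacts with "housing and community factors such as crime rate, transportation options, and perception of" children's safety.

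**The concern.** Section 4.5 and the form it describes disagree, and answers that are never asked for cannot be recovered later. Three consequences follow.

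- At least one planned Objective 8 analysis may have no input.
- The personal factor closest to the consumer-product analytes (parabens, triclosan, fragrance terpenes) is a child's own use of shampoo, soap or lotion. It is asked at a level that two siblings share, while Objective 1 is about why siblings in one home differ.
- A frequency scale that cannot tell an occasional user from a non-user blurs the product-to-concentration comparisons, most of all for substances that the protocol itself (section 4.3) describes as persisting indoors.

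**Working it through.** The plan states no figure on this point, so the check sets section 4.5 and the objectives beside Appendix C, items 1 to 31.

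**Promised content against the form**

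| Section 4.5 promises | Found in Appendix C |
|---|---|
| School as a location | No school or daycare column in item 3; the nearest is "Other indoor location". Item 11 (outdoor play at school or daycare) and item 17 (school meals) mention school but do not give time spent there. |
| How children moved between places | No travel-mode item. Item 3 has columns for vehicle, bus or train stop, street and parking garage. |
| Public-transport use | No item |
| Distance of visited places | No item |
| Perceived safety of visited places | No item |
| Sleep quality; outdoor areas at home | Present (items 13 and 10) |

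**Other sources for the missing content.** GPS is worn on Days 2 to 4, and the last of these is the day the questionnaire recalls (section 4.4.4). Distance could be derived from it, although the plan does not say so. The GPS model, as described under Objective 8, yields time at home and in vehicles, not time at school. Crime and transport options have extant community data as a source (sections 4.5 and 4.7; Table 8, Objective 11). A caregiver's perception of safety has none.

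**Product use within sibling pairs.** The rows number 11 (item 21) + 8 (item 22) + 9 (item 23) = 28, all asked for the home. Write the answer for child *i* in home *j* as x_ij = h_j + e_ij, where h_j is the household's true frequency and e_ij is reporting noise. The within-pair difference is

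d_j = x_1j − x_2j = e_1j − e_2j.

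If the caregiver answers both forms consistently, d_j = 0 in every home, for up to 64 pairs. The within-pair slope on the sibling difference in analyte y_j, Σ d_j·y_j / Σ d_j², is then 0/0. If the answers differ, d_j is noise only. In either case the 8 personal care rows carry no information on why siblings differ. They still vary between homes. Item 5 (grooming or bathing), item 14 (hand washing) and item 15 (bathing) are per child but name no product.

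**The merged category.** Objective 5 compares product categories reported as used with what is found in the media, by presence or absence and by frequency. Objective 4 feeds frequency into models that predict residential concentrations. A home with one application a year and a home with none receive the same code. The barcode and photo inventory (section 4.6) covers household cleaning and personal care products, so it helps with presence for 2 of the 9 classes in item 23. The other 9 − 2 = 7 classes, including pesticides, rest on the reported answer. Even for inventoried products, the inventory shows possession rather than use.

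**The case against.** The strongest reply is that most of what the objectives need is measured. For each child the study records half-hourly location and activity, floor and outdoor time, sleep, hand washing, bathing and diet, with GPS, accelerometer, hand wipes, socks and urine. Objective 5 is defined at residence level, so household product use is the right unit there. Section 4.5 states the household scope openly. The main-study questionnaires are not shown and may fill gaps. All of this stands, and it rules out four stronger readings that a reader might infer.

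- *The form has no school or transport items.* Not so: items 11 and 17 refer to school, item 3 records vehicle and near-road time, and GPS adds travel time. The gaps are narrower: school as a location, travel mode and public-transport use.
- *The child-level factors of Objectives 1, 5 and 8 are unmeasured, so Objective 1 cannot be tested.* Not so: the hypothesis covers activities and behaviours generally, and many of these can differ between siblings. Only reported product use cannot.
- *About a third of an index child's recorded time is unclassifiable.* The grid has 38 half-hours, or 19 h. An assumed school day of 6 to 7 h would be 6/19 = 32% to 7/19 = 37% of it. Those hours are still classified as indoors and away from home. They are pooled with other such places rather than lost, and only on school days.
- *The merged category defeats Objective 5.* The inventory supports presence for cleaning and personal care products, and pesticide residues, including piperonyl butoxide as a marker of pyrethroid use, are measured directly. The merge weakens the reported-use comparison; it does not remove the objective.

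The appeal to unseen forms stands only in part. Appendix A lists the main-study forms for the index child, the mother or caregiver and the home, not for the sibling, so nothing shown supplies sibling-level answers.

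**Conclusion.** The point holds as a mismatch between section 4.5, the instrument and specific analyses.

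- School time cannot be separated from other indoor places in the location grid.
- Travel mode, public-transport use, distance and perceived safety are promised but not asked. Of these, perceived safety leaves a planned Objective 8 analysis with no source in the documents shown.
- All 28 product rows are household-level, so the 8 personal care rows cannot contribute to the sibling comparison in Objective 1; other child-level factors can.
- Yearly users and never-users share a code, which weakens the reported-use parts of Objectives 4 and 5, chiefly for the 7 classes outside the inventory.

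This rests on the questionnaire in Appendix C being complete (items 1 to 31 run without a gap) and on the unseen main-study forms not asking the same questions about the sibling. It does not invalidate any objective as a whole, but it should be corrected before the form is first used.

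**What to change.** 1. Reword item 22 to ask about use on or by this child. Keep items 21 and 23 at household level.
2. In items 21 to 23, split the lowest answer into *a few times a year or less* and *never*.
3. Add a *School/daycare* column to item 3.
4. Either add the perceived-safety and transport items that section 4.5 describes, or delete the perceived-safety interaction from Objective 8 and the unmet promises from section 4.5. If distance is to come from GPS, say so.

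The cost is a minor questionnaire amendment with IRB review. Adding the safety and transport items would take about one extra minute per child (an estimate); the other changes add essentially no burden.

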4.6 Consumer Products Inventory

To generate an inventory of consumer products, the technician will photograph the locations where the participants indicate that household cleaning products and personal care products are stored. The technician will then send the pictures to EPA investigators (who will identify the products in the picture) using either email or multimedia messaging service. The technician will also inventory the products using a barcode scanner with memory. The image-based inventory (i.e., photograph) will be evaluated against the barcode-based inventory (i.e., technician collected

Appendix C (The IRB-approved Protocol)

inventory) to assess collection accuracy. The barcode-based inventory will serve as the standard against which the image-based inventory will be evaluated. For quality control purposes, collection of the consumer product use frequency information may be administered more than once.

4.7 Community-Level Data

Field technicians will identify, obtain, and organize community-level data as part of a feasibility assessment with potential future application across multiple Green Housing Study sites. There are a number of community-level domains that may be relevant with regard to participant activity location information, pollutant sources, and socioeconomic factors that may be directly or indirectly associated with asthma. Previous research has shown associations between some community-level factors and asthma. There is little research to assess to what extent these community-level factors might influence or distort analyses of asthma outcomes based on measurements obtained in traditional and renovated housing. Some of the community-level domains that might involve chemical or non-chemical stressor exposures to children include: pollutant sources; demographic; socio-economic; transit/transportation; land use/built environment; playgrounds/greenspace; safety/social disorder; household; education/school; medical access; food access utilization.

The field technicians will work to identify extant sources for these data, with an emphasis on geocoded data. Data sources including census, state and municipal, public health, and extant GIS datasets will be considered. It is beyond the scope of this pilot study to perform study-initiated community data collections or to perform land-use regression types of pollutant modeling assessments, but those could be considered in future study activities.

Appendix C (The IRB-approved Protocol)

5.0 DATA ANALYSIS PLAN

Our analysis approach will enable us to evaluate the objectives described in Section 2.0. Study participants will be characterized with regard to demographic variables such as age and gender as well as activity-related metrics from questionnaires and electronic devices. Housing and product information will be characterized based on questionnaire responses and technician information collection. Statistical analyses will be completed for target analytes and survey information at each study time point, as well as comparisons between time points and renovated/non-renovated homes. All media will be analyzed and compared between and among each media type. Cross-sectional, longitudinal, and pre/post renovation analyses will be conducted. Data quality (e.g., percent completion or detected, accuracy, precision) will be assessed to help make decisions on more complex statistical analyses that can be conducted with the available data.

Descriptive statistics, univariate analyses, and correlations will be employed to evaluate the pilot study data collected in the third study site. Descriptive statistics will be developed for all variables to be used in data analyses addressing the research objectives. Categorical variables will be summarized by frequencies, while continuous variables will be summarized by mean, standard deviation, median, and range. Environmental and biological measurement variables such as analyte concentrations in dust and urinary biomarker concentrations will be characterized by mean and standard deviation, median, range, appropriate distribution percentile values, and percent of measurements above the detection limit.

For detection limit censored data distributions, appropriate approaches for reducing bias in distributional parameter estimates will be considered (substitution, maximum-likelihood estimation, or beta-substitution, depending on the degree of censoring and sample sizes). Measurement distributions will be assessed for normality using the Shapiro-Wilks or other appropriate normality test. Depending on the distribution, measurement values may be log-transformed to compute geometric means and geometric standard deviations. Other types of transformations and/or non-parametric analysis methods will be considered if necessary.

Table 8 summarizes the data analysis plan, showing the relationship between the objective, data needed to evaluate the objective, and the proposed analysis approach.

As resources, time, and data suitability allow, additional analyses may be considered.

